At 0900 (0 min), the infusion will be varied so as to mimic the anticipated pattern of fall of EGP. In addition, glucose also labeled with [3-³H] glucose will be infused so as to maintain glucose concentrations at ~ 95mg/dL. Peripheral venous glucose concentrations will be measured every 10 minutes to allow the infusion rate of glucose to be adjusted as necessary.

Simultaneously, an infusion of somatostatin (60ng/kg/min) will be started at time 0 to inhibit endogenous islet secretion and therefore ensure identical portal insulin concentrations on the two study days(8). Insulin will be infused at a constant rate known to produce ~ 50% suppression of EGP (0.4mU/Kg/min).

From 0900 (0 min) to 1030 (90 min) no glucagon will be infused. Subsequently, a glucagon infusion will commence (91 – 180 min) at 0.35 ng/Kg/min and then increase to 0.70 ng/Kg/min (181- 270 min), a rate which will be maintained till the end of the study (1330).

Study B (0.8mU/Kg/min): Approximately 1-2 weeks after the first study visit, subjects will be asked to return to the CRTU. This study visit will be similar to Study A. However, insulin will be infused at 0.8mU/Kg/min 0 to 270 minutes.

Analytical Techniques: All blood will be immediately placed on ice, centrifuged at 4°C, separated and stored at -80°C until assay. Glucose will be measured using a Yellow Springs glucose analyzer. Glucagon will be measured using an ELISA (Mercodia, Winston-Salem, NC). C-peptide will be measured using EMD Millipore (Billerica, MA) reagents. Insulin will be measured using a chemiluminescence assay with reagents obtained from Beckman (Access Assay, Beckman, Chaska, MN). [3-³H] glucose specific activity will be measured by liquid scintillation counting following deproteinization(14). Endogenous glucose production (EGP) and glucose disposal (Rd) will be measured as before(9; 15).

Study A (Insulin 0.4mU/Kg/min):

Subjects will be admitted to the CRTU at approximately 1700 on the day prior to study. They will then consume a standard 10kcal/kg meal (55% carbohydrate, 30% fat, 15% protein, caffeine free) and fast overnight. Blood will then be sampled for baseline enrichment and ²H₂O (1.67g/kg of body water) will be given in 3 divided doses at 2200, 2400 and 0200 (13). The following morning (approximately 0530), a forearm vein will be cannulated to allow infusions to be performed. In addition, a

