Calculations: Glucose appearance and disappearance will be calculated using the steady-state equations of Steele et al., in which the actual tracer infusion rate for each interval is used in the calculation. The volume of distribution of glucose will be assumed to equal 200 ml/kg, and the pool correction factor assumed to be 0.65(16). Endogenous glucose production will be determined by subtracting the glucose infusion rate from the tracer-determined rate of glucose appearance(9). All rates of infusion and turnover will expressed per Kg/lean body mass.

Mean \pm SD	Detectable difference (0.4 vs. 0.8 insulin)	Detectable difference within each sub-group
Nadir EGP ($\mu\text{mol}/\text{kg}/\text{min}$)	3.9 ± 1.1	0.4 (10%)
AUC EGP ($\mu\text{mol}/\text{kg}$ per 5hr)	2816 ± 182	67 (2%)

Table 1: Pooled Means \pm SD used to estimate power. (Data from Ref. 1)

Statistical Analysis: A paired, two way student t-test (parametric) or a Wilcoxon matched-pairs

signed rank test (non-parametric) will be used to examine changes of EGP at the various time points of each study day. Differences between the 3 glucagon infusion rates will be assessed using a repeated-measures ANOVA which assumes the absence of a Gaussian distribution (Friedman test). Subsequently, in the presence of significant between group differences ($p < 0.05$), a *post-hoc* Student's t-test will used to examine differences between the 3 infusion rates of glucagon. If values are not normally distributed, a Dunn's test will be used instead.

Power calculation: Assuming similar variation to that previously observed(1), 60 subjects would provide approximately 80% power (at a 2-sided 0.05 α level), to detect small, biologically significant, differences in peak glucose, glucose area above basal and EGP in the presence and absence of glucagon suppression (Table 1, Col 3) as would 20 per subgroup (Table 1, Col 4).

D. Interpretation

We will accept our 1° hypothesis if endogenous glucose production (EGP) is higher during the 0.4 vs. the 0.8 study day. This would imply that despite rising glucagon concentrations higher insulin concentrations can still restrain EGP. It also will allow us to quantify the fold changes in EGP at low or high insulin concentrations.

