To test our 2° hypothesis we will express EGP at 80, 180 and 270 minutes as a percentage of fasting EGP (0 min). The relative changes with increments in glucagon will demonstrate whether the relationship is linear or asymptotic. Comparison of the two study days will enable us to determine the effect of insulin on this relationship. We will accept our 2° hypothesis if % suppression at the 80, 180 and 270 minute time points does not differ between study days.

We will calculate changes in nadir and integrated rates of EGP, as previously described(17-20), to compare suppression between the two study days. We will also undertake exploratory analysis of the rates of glucose disappearance (Rd) to determine if differences in glucagon concentrations affect Rd as well as EGP.

Limitations / Precautions/ Additional or Alternative Analyses:

- Inhibition of glucagon secretion by somatostatin lowers portal concentrations. In the case of glucagon, an infusion that maintains peripheral concentrations of glucagon constant likely will result in a ~10% decrease in portal glucagon concentrations(21-23). However, in the current experimental design, the portal glucagon concentrations on the two study days will not differ.

E. Human Subjects

Detailed Description: Suitable volunteers will be asked to visit the CRTU on a total of 3 occasions, including screening. During the first or screening visit they will meet with a member of the study team and undergo a history and physical examination to ensure that they fulfill entry criteria. If eligible, they will be asked to undergo determination of body composition. After an overnight fast, a cannula will be placed to allow IV infusion. Infusions will be started on the study days. In addition a retrograde hand vein for blood draws will be placed. This hand will be placed in a Perspex hot-box heated to about 120 °F. Blood will be sampled several times (via the retrograde hand vein) to obtain arterialized venous samples.

Population: Subjects will be recruited using intramural and local extramural advertising after approval from the Mayo Clinic Institutional Review Board. The racial composition of the county is outlined in the table below (%) using data from the 2000 population census. No children or prisoners will be recruited.

	American Indian or Alaskan Native	Asian or Pacific Islander	Black, not of Hispanic Origin	Hispanic	White, not of Hispanic Origin	Other	Total
Female	0.15	2.8	1.8	1.5	43.8	0	51.5

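### The plan promises to show whether the glucagon–EGP relationship is linear or asymptotic, but no planned analysis tests shape and no rule for naming it is given

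*Combined protocol and SAP*

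**What the plan says.** Under Study A in section C, glucagon is given in three consecutive periods. For the first, "From 0900 (0 min) to 1030 (90 min) no glucagon will be infused". After that, "a glucagon infusion will commence (91 – 180 min) at 0.35 ng/Kg/min and then increase to 0.70 ng/Kg/min (181- 270 min". The rates are therefore 0, 0.35 and 0.70 ng/kg/min, equally spaced, on both study days.

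Section D sets the scale for the secondary hypothesis: "we will express EGP at 80, 180 and 270 minutes as a percentage of fasting EGP (0 min". It then states: "The relative changes with increments in glucagon will demonstrate whether the relationship is linear or asymptotic". The next sentence uses the comparison of the two days to judge how insulin affects that relationship.

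The tests on the three rates are in the Statistical Analysis paragraph of section C. First: "Differences between the 3 glucagon infusion rates will be assessed using a repeated-measures ANOVA which assumes the absence of a Gaussian distribution (Friedman test". If that is significant, a Student's "t-test will used to examine differences between the 3 infusion rates of glucagon". Then: "If values are not normally distributed, a Dunn's test will be used instead". The same paragraph plans paired t or Wilcoxon tests of EGP at time points. No comparison of one step with the other, no trend or curvature contrast, no model fit and no rule for choosing between the two labels is given.

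**The concern.** With equally spaced rates, a linear response means two equal steps. The question is whether the step from 0.35 to 0.70 is smaller than the step from 0 to 0.35. The Friedman test asks whether any level differs from another, and the post-hoc tests ask whether two given levels differ. Neither compares the steps. A significant first step beside a non-significant second one is not evidence of a plateau, and two significant steps are not evidence of linearity.

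The shape, and its change with insulin, is one of the trial's stated products, and the text allows only two answers. The primary hypothesis expects a smaller glucagon response at the higher insulin rate. Smaller steps have less power, so an informal reading of the planned tests could turn a plain difference in response size into an apparent change of shape.

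**Working it through.** **The plan's own figure.** The documents give no error rate or precision for the shape statement. The nearest figure is the power statement: 60 subjects, about 80% power, nadir EGP SD 1.1 and detectable difference 0.4 (Table 1). As a paired calculation, n = ((1.960 + 0.842) × 1.1 / 0.4)² = 59.4, so it reproduces with 1.1 used as the SD of a paired difference.

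**Inputs.** From the documents: n = 15 (Study Subjects), SD 1.1 µmol/kg/min (Table 1), two-sided 0.05. Assumed, because the documents do not give them: correlation r between levels of 0.3–0.7, and equal true steps of 0.5–1.2 µmol/kg/min. The SD of a step is 1.1 × √(2(1 − r)), which is 1.1 at r = 0.5.

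**Assumed reading rule (not in the documents).** Asymptotic if the first step is significant and the second is not; linear if both are. Truth exactly linear, unadjusted paired t-tests, simulated. Cells show the percentage of trials called asymptotic, without / with the Friedman gate:

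| Step | r = 0.3 | r = 0.5 | r = 0.7 |
|---|---|---|---|
| 0.5 | 25 / 19 | 29 / 25 | 31 / 29 |
| 0.7 | 31 / 28 | 29 / 28 | 15 / 15 |
| 1.0 | 19 / 19 | 9 / 9 | 1 / 1 |
| 1.2 | 8 / 8 | 2 / 2 | 0.1 / 0.1 |

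The rate peaks where each step has about 50% power. Analytic check there, SD known and the two steps sharing the middle level (correlation −0.5): 1/4 + arcsin(0.5)/(2π) = 33%; with independent steps, 25%. Other error structures peak lower: 28 / 24 for AR(1) 0.5, 26 / 21 for AR(1) 0.8, 25 / 19 for independent steps. Bonferroni-adjusted t-tests still peak at 30%. Dunn's test, the plan's alternative, peaks at about 37%, for a step of 1.2 SDs of the paired difference.

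**Opposite error, same rule.** If 1.5 of a total rise of 2.0 µmol/kg/min occurs by 0.35 ng/kg/min, both steps are significant, and the response is called linear, in 28–56% of trials over r = 0.3–0.7.

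**Between days, same rule.** Take both days exactly linear, steps 1.0 and 0.6, r = 0.5, days independent, Friedman gate applied. The larger-response day is called linear in 81% of trials and the smaller-response day asymptotic in 29%. Both happen together in 0.81 × 0.29 = 23%.

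**Direct test.** The contrast is C = EGP(270) − 2 × EGP(180) + EGP(80).

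- A one-sample t-test on C calls a linear response attenuated in about 2.5% of trials whatever the step size.
- Its SD is 1.1 × √(6(1 − r)) = 2.25, 1.91 and 1.48 for r = 0.3, 0.5 and 0.7.
- The 95% CI half-width is 2.145 × SD/√15 = 1.25, 1.06 and 0.82.
- A complete plateau after a first step of 0.7 means C = −0.7, which is inside every one of those half-widths. A CI centred on zero would therefore not exclude even a full plateau, and linearity cannot be shown.
- In the three-quarters scenario above, its power is only 36–69%.

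**The case against.** The strongest objection is that the documents nowhere say shape will be read from p-values. Section D speaks of relative changes, which are magnitudes, and setting one increment against the other is close in spirit to C. This stands. A reader might infer that the plan mislabels about 30% of linear responses; the documents do not support that, because the rule behind the figure is supplied here. The rate is also a peak: at a step of 1.0 it is 1–19%. What remains is that the magnitudes come with no test, interval or rule, yet are said to settle the question.

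A reader might also infer that the only tests on the three rates are pairwise. They are not, since the Friedman test comes first; it lowers the peak slightly but carries no information on shape.

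Two points on scale stand in part. Section D uses percent of fasting EGP, whereas the calculations use absolute EGP with a pooled SD from an earlier study, labelled per kg, while this trial will express rates per lean body mass. Dividing a subject's three values by the same fasting value leaves equal steps equal, so the contrast carries over, but the half-widths do not. Equal spacing also holds for infusion rates, not necessarily for measured glucagon concentrations, so C is a sensible choice and not the only possible one.

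Finally, shape decides neither hypothesis. That limits the importance of the point but does not supply the missing analysis.

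**Conclusion.** The point holds as a gap between a stated conclusion and the planned analysis. No planned test addresses shape, no rule for naming it is given, and three rates in 15 subjects cannot establish linearity or an asymptote. Nothing above 0.70 ng/kg/min is studied, and the interval for curvature is about as wide as the steps themselves.

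The size depends on assumptions. Under the assumed significance-pattern rule, SD 1.1, correlation 0.3–0.7 and steps of 0.5–1.2 µmol/kg/min, a linear response would be called asymptotic in about 0–32% of trials by t-test, or 0–29% with the Friedman gate, against about 2.5% for a direct curvature test. Those rates show what an informal reading would risk; they are not properties of a procedure the plan specifies. The primary and secondary hypotheses are unaffected. The change is worth making because it costs little and the sentence as written promises more than the data can give.

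**What to change.** On each study day, compute for every subject (270 min) − 2 × (180 min) + (80 min) on the planned scale, EGP as a percentage of the fasting value, with absolute EGP as support. Report the mean with a 95% CI for each day, and the within-subject between-day difference in the contrast with its 95% CI. Report measured glucagon at each step so that the equal-spacing premise can be seen.

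Replace the shape sentence in section D with wording such as: *Shape will be judged by the curvature contrast. A 95% CI wholly below zero will be described as attenuation over the rates studied; a CI that includes zero will be reported as shape not determined, not as linear. An effect of insulin on shape will be judged only from the between-day difference in this contrast.* Drop the word asymptotic.

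The cost is one extra contrast and a change of wording, from data already collected, with no added subject, visit or assay. The downside is that the shape will often be reported as not determined. On the absolute scale the half-width is about 0.8–1.25 µmol/kg/min per day under the assumed SD and correlations, and about √2 times that (1.2–1.8) for the between-day difference if the two days' contrasts are uncorrelated.

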Study Subjects: We will recruit 15 otherwise healthy subjects using intramural and local extramural advertising after approval from the Mayo Clinic Institutional Review Board. Individuals who express interest in participating will be invited for a screening visit. Individuals with a BMI < 19 or > 40 kg/m² will be excluded from the study to avoid potential confounding effects that may result from extreme leanness or from obesity. Subjects will have no known systemic illness, taking any medication that could affect glucose metabolism and no history of upper gastrointestinal surgery.

Exclusion Criteria: Subjects < 18 years of age or > 60 years of age will not be studied to minimize the potential confounding effects of age on glucagon and insulin action. The subjects will not be taking medications that affect glucose metabolism (to be determined by PI) and have no history of chronic illness or upper gastrointestinal surgery. We are seeking to recruit subjects who do not have diabetes (fasting glucose <100mg/dL).

Screening Visit: To ensure subjects are healthy, following written, informed consent, subjects will undergo a history and physical examination, vital signs, height, weight, blood collection (after an 8 hour fast) for complete blood count, creatinine, sodium, potassium, fasting glucose and urine collection for point of care pregnancy testing for females able to become pregnant. Subjects will be instructed to consume a weight maintenance diet (55% carbohydrate, 30% fat and 15% protein, caffeine free) for at least 3 days prior to each study visit. **Body Composition:** Body composition will be measured prior to participation using dual-energy X-ray absorptiometry (iDXA scanner; GE, Wauwatosa, WI).

Experimental Design: Volunteers will participate in a total of 2 protocols. The overnight studies will be performed at least a week apart in random order.

cannula will be inserted retrogradely into a vein of the contra-lateral dorsum of the hand. This will be placed in a heated Plexiglas box maintained at around 120°F to allow sampling of arterialized venous blood. At approximately 0600 (-180 min), a primed, (10 μ Ci prime, 0.1 μ Ci/min continuous) infusion containing trace amounts of glucose labeled with [3-³H] glucose will be started and continued till 0900 (0 min).

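### The fixed ascending glucagon sequence cannot show whether the glucagon–EGP relationship is linear or asymptotic, because glucagon step and elapsed time are confounded within each day

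*Combined protocol and SAP*

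**What the plan says.** The glucagon schedule is under Study A in C. Research Design and Methods: "From 0900 (0 min) to 1030 (90 min) no glucagon will be infused", after which "a glucagon infusion will commence (91 – 180 min) at 0.35 ng/Kg/min and then increase to 0.70 ng/Kg/min (181- 270 min". For the other day, Study B states: "This study visit will be similar to Study A. However, insulin will be infused at 0.8mU/Kg/min 0 to 270 minutes". Randomisation, under Experimental Design, covers the days only: "The overnight studies will be performed at least a week apart in random order". Somatostatin starts at 0 min on both days. Insulin is constant within a day, and the lower rate is described thus: "Insulin will be infused at a constant rate known to produce ~ 50% suppression of EGP (0.4mU/Kg/min". The tracer infusion is varied from 0 min because EGP is expected to fall.

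D. Interpretation expresses EGP at 80, 180 and 270 min as a percentage of the 0 min value, which gives one reading per glucagon rate. It then states: "The relative changes with increments in glucagon will demonstrate whether the relationship is linear or asymptotic". Comparing the two days is meant to show how insulin alters that relationship.

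The Statistical Analysis paragraph gives a Friedman test across the three rates with post-hoc pairwise tests. It has no time term and no test of shape. The only limitation listed concerns portal glucagon concentrations.

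**The concern.** Each subject meets the three glucagon rates in one fixed order, during infusions that begin at 0 min. A later reading is always a higher-rate reading. Anything else that changes over the 270 minutes is carried into the step changes: onset of insulin action, duration of somatostatin, length of fast, or a waning glucagon effect. The second day repeats the sequence, so it does not help to separate rate from time.

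The sentence in D. Interpretation promises a conclusion about shape without qualification. The title-page rationale says the data will feed a model of insulin and glucagon contributions to glucose metabolism. A wrong shape, such as a saturating response read as linear, would carry forward into that model.

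**Working it through.** **The plan's own figure.** Nothing in the plan quantifies the shape analysis. The only figure that can be reproduced is the power statement: 60 subjects, nadir EGP difference 0.4, SD 1.1, two-sided 0.05. Taking the SD as that of the paired difference (an assumption), 0.4 × √60 / 1.1 = 2.82, and Φ(2.82 − 1.96) = 0.80. It reproduces, but it concerns nadir EGP and not a step change.

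**Step 1: structure, with no assumed physiology.** Time points are 80, 180 and 270 min; rates are 0, 0.35 and 0.70.
- Mean time is 176.67, so the deviations are -96.67, 3.33 and 93.33. Rate deviations are -0.35, 0 and 0.35.
- Correlation = (0.35 × 190) / √(0.245 × 18066.67) = 66.5 / 66.53 = 0.9995. The variance inflation factor is about 1084.
- A model with intercept, rate, rate squared and time has four parameters and rank 3.
- Because the rates are equally spaced, curvature is read from second step minus first step. That quantity equals (glucagon step 2 − glucagon step 1) + (drift over 180–270 − drift over 80–180). Only the sum is observed. Dividing by fasting EGP rescales it and separates nothing.

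**Step 2: illustration of size.** Assumptions: without glucagon, EGP as a percentage of fasting is 100 − 50 × (1 − 2^(−t/h)). The 50% is the protocol's approximate suppression at 0.4 mU/kg/min, taken as a plateau. The half-time h is assumed to be 20 to 60 min. Two true glucagon effects are added: linear (15 then 15 percentage points, true ratio 1.0) and saturating (15 then 7.5, true ratio 0.5).

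Example at h = 30: drift over 80–180 min is −50 × (2^(−80/30) − 2^(−180/30)) = −50 × (0.1575 − 0.0156) = −7.1 points.

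| h (min) | Drift 80–180 | Drift 180–270 | Linear: observed steps (ratio) | Saturating: observed steps (ratio) |
|---|---|---|---|---|
| 20 | -3.0 | -0.1 | 12.0, 14.9 (1.25) | 12.0, 7.4 (0.62) |
| 30 | -7.1 | -0.7 | 7.9, 14.3 (1.81) | 7.9, 6.8 (0.86) |
| 45 | -11.5 | -2.3 | 3.5, 12.7 (3.6) | 3.5, 5.2 (1.46) |
| 60 | -13.6 | -4.0 | 1.4, 11.0 (7.8) | 1.4, 3.5 (2.5) |

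With an assumed fasting EGP of 12 µmol/kg/min, drift over 80–180 min is 12 × 3.0% = 0.4 to 12 × 13.6% = 1.6 downward. Over 180–270 min it is about 0 to 12 × 4.0% = 0.5 downward. A truly linear effect can look accelerating, and a truly saturating one can look linear or accelerating.

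**Step 3: the favourable case.** At h = 10 min, drift over 80–180 min is about 6 × 2^(−8) = 0.02 µmol/kg/min. If insulin action is complete by 80 min, this source is negligible.

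**The case against.** **Insulin action may be complete by 80 min.** The first reading comes at 80 min, 10 minutes before glucagon starts, presumably to let suppression develop. The plan anticipates a fall in EGP but gives no time course for it. A 60-minute half-time would leave EGP at 8.4 of 12 at that point, only about 30% suppressed, which may be too slow. This stands as a limit on size: the documents do not establish that EGP is still moving at 80 min. Nor do they show that it has settled, and the other time effects remain aliased with rate.

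**Insulin-onset drift acts in one direction.** It shrinks the first step more than the second, so it would not create a false levelling-off. That is right for this source under this model. It can still hide a true levelling-off, and a waning glucagon effect could produce an apparent one.

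**Comparing days cancels time.** It does so only for drift common to both days. A reader might go further and infer that deeper suppression at 0.8 mU/kg/min must bias the between-day difference in the first step by 0.2 to 1.0 µmol/kg/min, against a planned detectable difference of 0.4. The documents do not support this:
- The range needs an assumed 80% plateau at 0.8 and the same half-time on both days. With 45 min at 0.4 and 30 min at 0.8, the drifts are -1.38 and -1.36, a difference near zero. With 60 and 20 min they are -1.63 and -0.58, and the sign reverses.
- The 0.4 is for nadir EGP with 60 subjects. The protocol plans 15, for which the same formula gives about 0.80 (0.86 by the t distribution).

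**Conclusion.** The sentence on linear versus asymptotic is wrong as written: it claims a property that the design lacks. The structural part (correlation 0.9995, rank 3 for four parameters) follows from the schedule alone. The drift figures rest on the assumed half-times, exponential form, fasting EGP of 12 and 50% plateau. They show that the conclusion on shape could be wrong in kind, not that it will be. The actual size and direction of the bias are unknown.

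A reader might infer that the hypothesis tests are undermined. They are not. The primary rule asks whether EGP is higher on the 0.4 than on the 0.8 day, and the secondary rule compares percentage suppression between days at matched times. Neither uses the within-day shape. The point is limited to the shape claim and to any comparison of step changes between days. It is worth correcting because it alters what the trial may conclude.

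**What to change.** 1. In D. Interpretation, replace the shape sentence with a statement that the within-day pattern across glucagon steps is descriptive and exploratory because step and time are confounded. Draw no linear-versus-asymptotic conclusion.
2. Add the fixed order and the absence of a constant-glucagon day to the listed limitations.
3. State that any between-day comparison of step changes assumes equal time drift on the two days.
4. Prespecify the change from 180 to 270 min as a sensitivity contrast, noting that it reduces insulin-onset drift but not every time effect.

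Relating EGP to measured plasma glucagon instead of infusion rate would not replace these changes, since measured glucagon would also be expected to rise with time.

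The cost is wording, one extra contrast and a weaker dose-response claim. No visit or procedure is added.

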Title

**The Effect of the Interaction of Glucagon and Insulin on Endogenous
Glucose Production in Humans**

Protocol Number: 20-001570

Principal Investigator: [name]

IND Sponsor: [name], # 116569 (Somatostatin)

Funded by: Intramural Funds

Version Number: 2

January 13, 2021

NCT: 04461015

Specific Aim: Determine the relative contribution of changes in insulin and glucagon concentration on endogenous glucose production in nondiabetic subjects.

1° Hypothesis: Hyperinsulinemia restrains the effect of rising glucagon concentrations on endogenous glucose production

2° Hypothesis: The % change in endogenous glucose production in response to rising glucagon concentrations is unchanged by hyperinsulinemia

Rationale: The experimental design we propose will enable the dissection of the relative contribution of insulin and glucagon concentrations to endogenous glucose production. Acquisition of this data will allow us to develop a model of insulin and glucagon contributions to postprandial glucose metabolism (1; 2).

A. Significance

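### The secondary hypothesis of no change is accepted on failure to find a difference, with no equivalence margin and only 15 subjects

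*Combined protocol and SAP*

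**What the plan says.** The secondary hypothesis, on the opening page, is a statement of no effect: "The % change in endogenous glucose production in response to rising glucagon concentrations is unchanged by hyperinsulinemia". Section D (Interpretation) gives its decision rule: "We will accept our 2° hypothesis if % suppression at the 80, 180 and 270 minute time points does not differ between study days". The endpoint is EGP at those three times as a percentage of the fasting value at 0 min.

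The Statistical Analysis paragraph in section C lists a paired t-test or Wilcoxon signed rank test, which "will be used to examine changes of EGP at the various time points of each study day". For the three glucagon rates it lists a Friedman test with post-hoc comparisons. All of these test for a difference. The Power calculation likewise concerns the ability "to detect small, biologically significant, differences in peak glucose, glucose area above basal and EGP" with 60 subjects, whereas under Study Subjects the plan says "We will recruit 15 otherwise healthy subjects". No equivalence margin, equivalence test or confidence-interval criterion appears anywhere.

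**The concern.** A non-significant difference test does not show that two conditions are the same. It may only mean that the data were too imprecise to separate them. Under this rule, more assay noise, fewer completers or a smaller sample all make acceptance more likely, which is the wrong direction for a claim of no change.

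At stake is one of the study's two stated hypotheses. An inconclusive comparison would be written up as the positive finding that the percentage response of EGP to glucagon does not depend on insulin. The opening rationale says the data will feed a model of insulin and glucagon contributions to glucose metabolism, so the error could carry into that model.

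**Working it through.** **Inputs.** Table 1: nadir EGP 3.9 ± 1.1 µmol/kg/min, detectable difference 0.4 (10%); AUC EGP 2816 ± 182 µmol/kg per 5 hr, detectable difference 67 (2%). Power calculation: 60 subjects, about 80% power, two-sided 0.05. Study Subjects: 15. The plan gives no SD for EGP as a percentage of fasting, so Table 1 serves as a proxy on the raw scale.

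**Step 1: reproduce the plan's figure.** Take the tabulated SD as the SD of the paired difference, with n = ((z₀.₉₇₅ + z₀.₈₀) × SD/δ)².
- Nadir: (2.802 × 1.1/0.4)² = 59.4, so 60.
- AUC: (2.802 × 182/67)² = 57.9, so 58.

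Paired-t power at n = 60 is 79% (nadir) and 80% (AUC). This reading reproduces the stated 60. An unpaired comparison would need 119 and 116 per arm and does not.

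**Step 2: one test at n = 15.** The standardised differences are 0.4/1.1 = 0.364 and 67/182 = 0.368. Noncentral-t power with 14 degrees of freedom is 26% on both rows, so a difference of that size is called non-significant about 74% of the time. The 95% CI half-width for nadir EGP is 2.145 × 1.1/√15 = 0.61, or 16% of 3.9. An estimate just short of significance would have an interval from about 0 to 1.2, or 31% of the mean, and would still count as no difference.

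**Step 3: the full rule (all three tests non-significant), by simulation at n = 15.**

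| True difference (nadir scale) | Correlation between times 0 | 0.5 | 0.8 |
|---|---|---|---|
| none | 86% | 87% | 90% |
| 0.4 at all three times | 41% | 52% | 60% |
| 0.4 at one time only | 67% | 68% | 70% |
| 0.8 at all three times | 2% | 7% | 13% |

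The AUC row, with 67 at all three times, gives 40% to 60%. Dividing the first line by the second gives 0.86/0.41 = 2.1, 0.87/0.52 = 1.7 and 0.90/0.60 = 1.5. Acceptance is thus only 1.5 to 2.1 times as likely under no change as under a difference that the plan itself calls biologically significant.

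**Step 4: where the problem shrinks.**
- *80 minutes.* Under Study A, "From 0900 (0 min) to 1030 (90 min) no glucagon will be infused", so the 80-minute comparison reflects the insulin contrast alone and may separate the days. With 0.4 at 180 and 270 min and a difference of 0.8, 1.0 or 1.2 at 80 min, acceptance falls to 14–25%, 5–9% or under 3%.
- *AUC precision.* The AUC SD is 182/2816 = 6.5% of the mean. A 10% difference is then missed in fewer than 0.1% of single tests.
- *SD reading.* If 1.1 is a between-subject SD with within-subject correlation r, the SD of the difference is 1.1 × √(2(1 − r)). Power for 0.4 at n = 15 is 15% at r = 0, 26% at r = 0.5 and 83% at r = 0.9.
- *Percentage scale.* For an assumed paired SD of 10, 20 or 30 percentage points, one test misses a true 10-point difference 5%, 56% or 77% of the time.

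**The case against.** The strongest reply is that the size is unknown. The endpoint is a percentage of fasting EGP, whereas Table 1 gives raw nadir and AUC values from an earlier study, captioned as pooled means and SDs. The results in step 4 range from serious to negligible. This stands: the rates are illustrations, not estimates for this endpoint.

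Second, requiring all three times to agree is strict. If the primary hypothesis is true and fasting EGP is similar on the two days, the percentage of fasting EGP should also differ, especially at 80 min, so the rule may seldom accept. This also stands as a point about frequency. It further shows that, because the 0-min denominator precedes the insulin infusion, the endpoint mixes suppression by insulin with the response to glucagon.

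Third, section D names no test for the between-day comparison of percentage suppression. That is correct, and reading the rule as non-significance is an inference. It is the only reading the document supports, since every test it lists is a test for a difference.

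None of these points supplies a margin. They bear on how often the rule would mislead, not on whether it can support the conclusion drawn from it.

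**Conclusion.** The concern holds and should be fixed. The rule that percentage suppression "does not differ between study days" cannot establish the secondary hypothesis, because it equates lack of significance with lack of effect. On the nadir row, with 1.1 as the SD of the paired difference and 0.4 present at all three times, false acceptance is about 41% to 60%. It is lower if the true differences are larger, if the 80-minute insulin effect is large, or if paired precision is nearer the AUC row. The defect in the rule depends on none of these assumptions. The primary hypothesis test is not affected.

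**What to change.** Delete the acceptance rule in section D and replace it with text such as:

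> For EGP as a percentage of fasting EGP at 80, 180 and 270 min, the paired between-day difference will be reported at each time point with its 95% CI. A non-significant difference will be described as inconclusive. The response will be described as unchanged only if the 90% CI lies wholly within a pre-specified equivalence margin at every time point the claim covers.

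The margin must be justified and fixed before the data are analysed, and the text should name the time points covered. The document gives no basis for a margin. If none can be justified, drop the last sentence of the replacement text and report estimates and intervals alone.

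**Cost.** The estimate-and-interval version changes wording only: no extra subjects, visits or assays. The price is that a claim of no change becomes harder to make with 15 subjects. On the nadir proxy, with zero true difference, the criterion would be met as follows:

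| Margin (% of 3.9) | One time | Two times | All three |
|---|---|---|---|
| ±10% | about 2% | under 1% | under 1% |
| ±20% | about 67% | 44–54% | 30–46% |
| ±25% | about 89% | 80–84% | 71–80% |

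Ranges cover between-time correlations of 0 to 0.8. With the AUC row's SD, ±10% would be met more than 99% of the time.
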